**Subsequent visits: (4,8,12 months)**

- Have in-office BP obtained by a trained research assistant using a standardized protocol mentioned above.
- Complete health-related surveys (see full list of measures in section 5.5). Surveys may also be administered by telephone or by mail if Veteran is unable to complete the research visit in-person, but priority will be given to in-person survey administration.
- Measurement of vitals: weight, waist circumference
- Have blood drawn at VA lab to measure lipid panel. If lipid panel has been completed in the past 28 days, will not need to repeat during follow-up visit.

**Randomization:** Study statisticians will develop a 1:1 blocked randomization scheme, stratified by site and hyperlipidemia status. The project coordinator and research assistant will be blinded to the randomization schema and will randomize each subject using an automated randomization methods embedded in the study tracking software. Participants will be randomized to one of two groups:

- Education control group
- Intervention

[figure not shown]
**Education control group:** Participants assigned to the education group at baseline will receive usual care enhanced with general prevention education delivered by the research assistant in person at lab collection times (0, 4, 8, and 12 months). Providers will not be able to see research outcome assessment of BPs since these are not placed into CPRS.

We believe it would be unethical to use a usual care comparison group. The Education control group is receiving more than usual care: education material given at each visit, BP monitored and documented in CPRS, and providers notified if BP exceeds safety thresholds, requiring their co-signature.

**Intervention:** Participants assigned to the intervention will also complete in-person visits every 4 months, as listed above but will also have additional contact with our interventionist who may be either a nurse or pharmacist. The in-person visits will be identical to those in the education control group, but without the in-person education material. At their baseline visit, individuals enrolled in the intervention will be invited to consent and enroll in the VA Annie program, allowing them to submit home BP readings via text message before their intervention contacts. This is an existing VA program, but will not be required to participate in the intervention.

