where  $Y_{ij}$  represents the outcome of interest (i.e., SBP or non-HDL) for patient  $i$  at time  $j$ . We will fit a common intercept and arm is the intervention group indicator. Similarly, time will be classified, where for example,  $I(month = 12)$  is a dummy variable equal to 1 for the 12 month time point. Random intercepts will be included for each individual to account for correlation among repeated measurements over time. The primary analytic model will adjust for clinic site and hyperlipidemia status. The mixed effects model parameters will be estimated and tested using SAS PROC MIXED (SAS Institute, Cary, NC), and the hypothesis of between-arm differences over time will be tested using estimate statements within PROC MIXED. In particular,  $\beta_7$ , the estimated difference in outcome between arms at 12 months, will be the primary effectiveness outcome

assessed. All analyses will be conducted following an intention to treat (ITT) principle.

**Missing data.** We will assess mechanisms for missing data in this study. LMM, implicitly accommodates missingness when the response is Missing At Random (MAR); that is, when missingness is due either to treatment, to prior outcome, or to other baseline covariates included in the LMM.

Our primary analysis will include all available study-collected data. A sensitivity analysis will be conducted by filling in missing data in the following manner:

1. Use all available study-reported data.
2. If missing study-reported value → use the SBP or non-HDL cholesterol value if available in the EMR in a 2 month window from the target data for that time point
3. If missing EMR-reported value → assess whether the outcome has >10% missing remaining.
  - a. If yes, ≥10% missing → use multiple imputation
  - b. If no, <10% missing → do not use multiple imputation, include only study- and EMR-reported values

The final determination whether to use multiple imputation is separate for SBP and non-HDL cholesterol outcomes; SBP could meet the criteria and non-HDL does not, or vice versa.

If multiple imputation is indicated, we will use multiple imputation procedures as described by Schafer. Once missing values have been imputed, each multiply-imputed data set can be analyzed using the LMM. Final parameter estimates and their standard errors will be calculated using Rubin's formula.

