Principal Investigators: [name] PhD

Deliverable (e.g., manuscript, report): Manuscript

Covariates for Descriptive, Matching or Regression Purposes:

Stratification Variables:

Variable	Description	Variables and Source	Specifications
Site	Site where Veteran was randomized; stratification variable	REDCap: site	Atlanta, Baltimore, Cleveland, Durham
Hyperlipidemia	Hyperlipidemia status at randomization; stratification variable	REDCap: HYPERLIPIDEMIA_2	0 = No Hyperlipidemia 1 = Hyperlipidemia

Descriptive Clinical Outcomes:

Outcome	Description	Variables and Source	Specifications
SBP	Baseline 4m 8m 12m	Long: systolic Wide: systolicbase, systolic4, systolic8, systolic12	Continuous
DBP	Baseline 4m 8m 12m	Long: diastolic Wide: diastolicbase, diastolic4, diastolic8, diastolic12	Continuous
Non-HDL Cholesterol	Baseline 4m 8m 12m	Long: Nonhdl Wide: nonhdlbase, nonhdl4, nonhdl8, nonhdl12	Continuous
Cholesterol	Baseline 4m 8m 12m	Wide: choltotalbase, choltotal4, choltotal8, choltotal12	Continuous
HDL	Baseline 4m 8m 12m	Long: hdl Wide: hdlbase, hdl4, hdl8, hdl12	Continuous
LDL	Baseline 4m 8m 12m	Long: ldl Wide: ldlbase, ldl4, ldl8, ldl12	Continuous

Some of these are specific to clinical trials (based on this [JAMA paper](#)) and some are other are specific to observational studies (based on [STROBE/RECORD](#) guidelines),

Statistical Analysis Plan

Project: A nurse-led intervention to extend the Veteran HIV treatment cascade for cardiovascular disease prevention (V-EXTRA-CVD)

Principal Investigators: [name] PhD

Deliverable (e.g., manuscript, report): Manuscript

Other Variables:

Variable	Description	Variables and Source	Specifications
ID		Record_id	
Sex		Demog_sex	1 = Male 2 = Female
Gender		DEMOG_GENDER	1 = Man 2 = Woman 4 = Transgender Woman
Sexual orientation		SEXUALORIENTATION	0 = Other 1 = Heterosexual
Race		RACE	0 = White 1 = Black or African American 2 = Other
Ethnicity		DEMOG_HISPANIC	1 = Yes 2 = No 3 = Don't Know
Education		EDUCATION	1 = High school or less 2 = Some college or trade school 3 = College graduate or higher
Employment Status		EMPLOYMENT	0 = Employed 2 = Unemployed 3 = Retired
Marital Status		MARRIED	0 = Not married 1 = Married 2 = DK/Missing
Financial Status		FINANCIAL	0 = No financial troubles 1 = Financial troubles
Housing or Food Insecurity		HOUSEFOODINSECURE	0 = No housing or food insecurity 1 = Housing or food insecurity
Rurality		GISURH	H = Rural R = Rural U = Urban

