where Y_{ij} represents the outcome of interest (i.e., SBP or non-HDL) for patient i at time j . We will fit a common intercept and arm is the intervention group indicator. Similarly, time will be classified, where for example, $I(month = 12)$ is a dummy variable equal to 1 for the 12 month time point. Random intercepts will be included for each individual to account for correlation among repeated measurements over time. The primary analytic model will adjust for clinic site (reference: Durham) and hyperlipidemia status. The mixed effects model parameters will be estimated and tested using SAS PROC MIXED (SAS Institute, Cary, NC), and the hypothesis of between-arm differences over time will be tested using estimate statements within PROC MIXED. In particular, β_7 , the estimated difference in outcome between arms at 12 months, will be the primary effectiveness outcome assessed. All analyses will be conducted following an intention to treat (ITT) principle using all available data.

We will examine the observed trajectories of outcome measurements over time to determine if the overall slope is also of interest.

Update 5/9/2025: instead of using a random intercept for each person (which essentially assumes a CS covariance structure), we will use a repeated statement with an unstructured covariance matrix. This is more flexible than CS and works well with a limited number of time points.

Secondary Analyses:

The secondary outcome will be non-HDL cholesterol at 12 months and use the same model structure listed in the primary outcome section.

Some of these are specific to clinical trials (based on this [JAMA paper](#)) and some are other are specific to observational studies (based on [STROBE/RECORD guidelines](#)),

Statistical Analysis Plan

Project: A nurse-led intervention to extend the Veteran HIV treatment cascade for cardiovascular disease prevention (V-EXTRA-CVD)

Principal Investigators: [name] PhD

Deliverable (e.g., manuscript, report): Manuscript

Update 5/28/2025: Since hyperlipidemia is strongly correlated with cholesterol, this term has been omitted from the models with non-HDL cholesterol as the outcome. While including randomization stratification variables can help with precision, it is better to omit this variable from these models.

Sensitivity Analysis/Missing Data:

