We will assess mechanisms for missing data in this study. LMM implicitly accommodates missingness when the response is Missing At Random (MAR); that is, when missingness is due either to treatment, to prior outcome, or to other baseline covariates included in the LMM.

Our primary analysis will include all available study-collected data. We will first examine the amount of missingness at each timepoint for each of the two outcomes. We may impute missing values using multiple imputation procedures as described by Schafer. Each imputed dataset will be analyzed with the LMM model, and final parameter estimates and their standard errors will be calculated using Rubin's formula.

Notes on the protocol: The original protocol specified the following plan to fill in missing data (doing this process separately for each outcome):

1. Use all available study-reported data
2. If missing study-reported value, use the SBP or non-HDL cholesterol value if available in the EMR in a 2-month window from the target data for that time point.
3. If missing EMR-reported value, assess whether the outcome has >10% missing remaining
 - a. If yes, $\geq 10\%$ missing, use multiple imputation
 - b. If no, $<10\%$ missing, do not use multiple imputation, include only study- and EMR-reported values.

Updated plan: We will not plan to use EMR data for SBP due to concerns about the consistency of these measurements in different settings. For example, SBP may vary, with lower values observed in calmer settings. On the other hand, non-HDL cholesterol may be more consistent which could allow us to use EMR data. In addition, we will not use 10% as a strict threshold for imputation as it is unclear if this is 10% missing at each time point or overall. We will instead examine if characteristics vary by retention status at each time point. For example, there may be variables highly related to missingness but <10% missingness; in such a case, we may still want to impute missing values. Any baseline characteristic found to be associated with missingness at any time point will be included in the imputation model.

Attrition bias: As part of our examination of missing data, we will assess differences in baseline characteristics (e.g., clinic site, demographics, clinical values, medical history) by retention at each follow up time point. We will use two sample t-tests (or Wilcoxon rank sum tests) for continuous variables and chi-squared tests (or Fisher's exact test) for categorical variables.

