Subgroup Analyses:

Pre-specified sub-group analyses of the primary and secondary outcomes will include clinic site (reference: Durham), sex (reference: male), and baseline ASCVD risk category (<20%, $\geq 20\%$) (reference: low risk). For each category, we will examine the interactions with intervention arm and time. Generally, the modeling approach will mirror that described above for each outcome. Three separate analyses for each outcome will be conducted to assess the effect of each potential moderator. Models will be fit in SAS PROC MIXED, as described above, and the moderating effect of each of the three factors will be assessed via the hypothesis test of the three-way interaction among subgroup, treatment, and time at 12 months. We may also report the results for time at 4 months and time at 8 months if this is of interest.

Some of these are specific to clinical trials (based on this [JAMA paper](#)) and some are other are specific to observational studies (based on [STROBE/RECORD guidelines](#)),

Statistical Analysis Plan

Project: A nurse-led intervention to extend the Veteran HIV treatment cascade for cardiovascular disease prevention (V-EXTRA-CVD)

Principal Investigators: [name] PhD
Deliverable (e.g., manuscript, report): Manuscript

An example model for sex is as follows, with the addition of the main effect for sex, interactions between sex and study visit, and interactions between sex, study visit, and treatment arm.

$$Y_{ij} = \beta_0 + \beta_1 * I(month = 4) + \beta_2 * I(month = 8) + \beta_3 * I(month = 12) + \beta_5 * arm * I(month = 4) + \beta_6 * arm * I(month = 8) + \beta_7 * arm * I(month = 12) + \beta_8 * clinic + \beta_9 * hyperlipidemia + \beta_{10} * sex + \beta_{11} * I(month = 4) * sex + \beta_{12} * I(month = 8) * sex + \beta_{13} * I(month = 12) * sex + \beta_{14} * arm * I(month = 4) * sex + \beta_{15} * arm * I(month = 8) * sex + \beta_{16} * arm * I(month = 12) * sex$$

Additional Analyses:

We decided to add additional, post-hoc analyses examining the moderating effects of “out of control” baseline SBP (baseline SBP \geq 140) and race. The same approach from the subgroup analysis section will be used here.

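### The SAP drops hyperlipidemia, a randomisation stratum, from the non-HDL models because it correlates with the outcome. That reason favours keeping it, but the cost is small: about 0–2% in the reported standard error.

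*SAP*

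**What the plan says.** Protocol 5.1 (Randomization) specifies a "1:1 blocked randomization scheme, stratified by site and hyperlipidemia status". The SAP's table of stratification variables describes the factor as "Hyperlipidemia status at randomization; stratification variable". Protocol 5.6 (Aim 2 analysis) states: "The primary analytic model will adjust for clinic site and hyperlipidemia status". Both documents define the model's response as either SBP or non-HDL. The SAP equation carries hyperlipidemia as one constant term (beta 9), with no interaction with month.

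The SAP's Secondary Analyses section first gives non-HDL the same model structure. The update of 5/28/2025 then says: "Since hyperlipidemia is strongly correlated with cholesterol, this term has been omitted from the models with non-HDL cholesterol as the outcome". It continues: "While including randomization stratification variables can help with precision, it is better to omit this variable from these models". No other reason is given. Site, the other stratification factor, stays in.

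Two further sections are affected. The missing-at-random statement counts only covariates in the model: "that is, when missingness is due either to treatment, to prior outcome, or to other baseline covariates included in the LMM". For subgroups, "Generally, the modeling approach will mirror that described above for each outcome"; the example equation there still prints the hyperlipidemia term.

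Protocol 5.1 (Aim 2, Participants) defines hyperlipidemia as non-HDL above the National Lipid Association target, or lipid-lowering medication, based on the last 3 years. Participants are randomised at the baseline visit, and a panel from the previous 28 days may replace the baseline draw. The documents do not say which non-HDL value sets the stratum.

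**The concern.** The factor is fixed before treatment starts and balanced between arms by blocked allocation, so its correlation with cholesterol is not collinearity with treatment. Association with the outcome is the usual ground for including a pre-randomisation covariate. The SAP concedes that such covariates can help precision, then calls omission better without naming a benefit. The update therefore departs from the protocol model for a reason that points the other way.

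At stake is a standard error that matches the way patients were allocated. The form of the term also matters. Month-0 non-HDL is a response in this model, and the stratum is partly defined by non-HDL. If the gap between strata is widest at month 0 and then shrinks, a constant term fits badly.

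**Working it through.** **Inputs from Protocol 5.6 (Power).** N = 300, SD 41 mg/dL, within-person correlation 0.7, missing 5/10/15% at months 4/8/12, two-sided 0.05. **Not in the documents, assumed:** hyperlipidemia prevalence 60%; stratum explains 5, 10 or 20% of non-HDL variance.

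**Formula.** Var(b) = [sum of n X'V⁻¹X]⁻¹, summed over arm, stratum and dropout pattern (5% leave after month 0, 5% after month 4, 5% after month 8, 85% complete). X holds the common intercept, three month terms and three arm-by-month terms. V is compound symmetric. Site is left out, being common to all versions.

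**Step 1: reproduce the plan.** Without a stratum term, N × Var = 3,946.6, so the SE at N = 300 is √(3,946.6/300) = 3.627.
- N for 15 mg/dL at 90% power: (1.960 + 1.282)² × 3,946.6/15² = 184. Table 4 gives 184.
- N for 10 mg/dL at 80% power: (1.960 + 0.842)² × 3,946.6/10² = 310. Table 4 gives 310.
- Power for 15 mg/dL at N = 300: Φ(15/3.627 − 1.960) = 98.5%. The protocol says above 90%.
- One cell differs more (15 mg/dL at 80%: 138 against 148). It looks like simulation noise and does not affect this point.

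**Step 2: stable gap between strata.** The gap d satisfies 0.6 × 0.4 × d² = R² × 41², so d = 18.7, 26.5 and 37.4 mg/dL. Including the factor removes 0.24d² from every element of V.

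| Variance explained | Omitted | Constant or by-month | Excess from omission |
|---|---|---|---|
| 5% | 3.627 | 3.611 | 0.4% |
| 10% | 3.627 | 3.593 | 0.9% |
| 20% | 3.627 | 3.551 | 2.1% |

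Power for 10 mg/dL rises from 78.7% to 79.1–80.4%. For 15 mg/dL it is at least 98.5% either way.

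**Step 3: gap falls linearly to half by month 12**, within-stratum covariance held fixed.

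| Variance explained at month 0 | Omitted | Constant | By-month |
|---|---|---|---|
| 5% | 3.617 | 3.642 | 3.611 |
| 10% | 3.603 | 3.654 | 3.593 |
| 20% | 3.561 | 3.666 | 3.551 |

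The constant term is now 0.7–2.9% worse than omission; by-month terms are 0.2–0.3% better.

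**Step 4: simulate how the stratum is set.** 1,500 trials per definition, permuted blocks of 4 within strata, unstructured covariance by REML as in the SAP update of 5/9/2025. A 130 mg/dL cut-off and 40% medicated are assumptions. Mean reported SE:

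| Stratum set by | Omitted | Constant | By-month |
|---|---|---|---|
| Month-0 value or medicated | 3.613 | 3.670 | 3.613 |
| Month-0 or one earlier value, or medicated | 3.614 | 3.612 | 3.598 |
| Earlier value or medicated | 3.619 | 3.570 | 3.571 |
| Any of three earlier values, or medicated | 3.617 | 3.556 | 3.557 |
| Month-0 value only | 3.614 | 3.766 | 3.615 |
| Earlier value only | 3.615 | 3.476 | 3.477 |

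The first four rows keep the medication limb of the protocol definition. There the excess from omission over by-month terms runs from nil to 3.617/3.557 − 1 = 1.7%. Only the last row gives about 4% (3.615/3.477 − 1 = 4.0%).

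**Step 5: validity.** Across the simulated definitions, bias was at most 0.10 mg/dL (Monte Carlo error 0.09) and coverage 93.9–96.2% for all three models. A separate null simulation used 6,000 trials with stratified allocation, prevalence 0.7 and a gap of 30 mg/dL. Type I error was 4.9% with omission and 5.2% with by-month terms. The actual standard deviation of the estimate was 3.376 in every model, while the mean reported SE was 3.374 omitted and 3.335 by-month.

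**The case against.** The best case for the SAP is that both models are valid and the choice hardly matters. Month-0 non-HDL is already in the response vector with a common intercept and absorbs most of what the stratum would add. The only documented alternative is the constant term, and Steps 3 and 4 show that it can lose to omission, so calling omission better is defensible against the model on paper. By-month terms appear in neither document. The gain also depends on prevalence, gap and stratum source, none of which is stated. The change is dated and disclosed.

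Much of this stands, and it is why the point is low priority. It does not rescue the stated reason, and it is an argument for choosing the right form of the term: by-month terms were never more than 0.1% worse than omission in any scenario run.

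Two supporting arguments are weak. Loss of the factor from the missing-at-random covariates matters little, because prior outcomes still count. With 12-month dropout of 25% in the intervention-arm hyperlipidemia stratum and 10% elsewhere, omission moved the estimate by at most 0.25 mg/dL. Lipid management given only in the intervention arm would produce arm-specific shrinkage, which by-month terms without arm do not describe.

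A reader might infer that omission biases the effect or invalidates the test. Step 5 shows neither. A reader might also infer from the 2025 date that the change followed sight of results. The documents do not say whether non-HDL had been examined by arm, so this cannot be concluded.

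**Conclusion.** The concern holds in a limited form. The stated rationale is unsound, and the omission departs from the protocol model. The consequence is a reported 12-month non-HDL standard error that may be about 0–2% too large under the documented stratum definition. It would be about 4% only if an earlier laboratory value alone set the stratum, and nil if the month-0 value set it. The sizes rest on the assumed prevalence, gap, cut-off and medicated share.

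The benefit of keeping the factor is mainly a standard error that reflects the stratified design; the estimate itself is hardly less variable. A reader might take the 4% as the expected gain, but that case ignores the medication limb of the definition. This is a secondary outcome with about 98% power for 15 mg/dL, and no conclusion about that effect is expected to change.

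**What to change.** Withdraw the correlation rationale. Keep site and hyperlipidemia in the non-HDL model and its subgroup models, entering hyperlipidemia as a main effect plus hyperlipidemia-by-month terms. Do not restore the constant term alone. Record this as a dated change from the protocol and the SAP equation, and report the model without hyperlipidemia as a sensitivity analysis. State which non-HDL value, and from what date, sets the stratum. If non-HDL results by arm have already been seen, say so and show both models.

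The cost is one SAP paragraph, four degrees of freedom (one main effect and three interactions) and a re-run of the non-HDL models.
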